15.29 Nursing Guidelines

- 15.291 Agent is known to be teratogenic in rabbits. Therefore all women who are pregnant or who could become pregnant, should not handle the agent outside of the original packaging. Chemotherapy gloves should be worn if contact is necessary.
- 15.292 Because of the similarity of this agent to thalidomide certain precautions MUST be employed by all subjects on protocol and for 4 weeks after discontinuation of agent. Instruct patients the following must be adhered to: No donation of tissue/blood/semen/sperm; sexually active males/ females must use protocol-specific contraception (regardless of fertility status- i.e. history of vasectomy).
- 15.293 Cytopenias are common (neutropenia most common). Monitor CBC closely and instruct patient to report any signs/symptoms of infection or unusual bruising or bleeding to the study team.
- 15.294 Thrombotic events have been reported. Anticoagulation prophylaxis may be recommended. Instruct patients to report any problems with bleeding, extremity pain or swelling, or shortness of breath to the study team immediately.
- 15.295 Patients may experience cough, URI, pneumonia, or sinusitis. Instruct patients to report respiratory symptoms to the study team.
- 15.296 Gastrointestinal side effects consisting of diarrhea, constipation, stomatitis, nausea, decreased appetite, and abdominal pain have been seen. Treat symptomatically and monitor for effectiveness.
- 15.297 Drug should be taken without food (at least 2 hours before or 2 hours after a meal). Do not open or crush capsules.
- 15.298 Patients may experience myalgias and muscle spasms. Treat symptomatically and monitor for effectiveness.
- 15.299a Fatigue is common. Instruct patient in energy conserving lifestyle.
- 15.299b Warn patients about the possibility of peripheral neuropathy, headache, confusion, and dizziness.
- 15.299c Patients may experience URI, pneumonia, dyspnea, and cough. Instruct patients to report respiratory symptoms to the study team.
- 15.299d Severe dermatologic reactions have been seen (including urticaria). Instruct patient to report and rash or skin changes to the study team.
- 15.299e All patients must be registered in the POMALYST REMS program. See protocol for more details.

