3.0 Patient Eligibility

3.1 Inclusion Criteria

- 3.11 Age ≥ 18 years.
- 3.12 Previously treated ASCT naïve MM patients, currently with relapsed or refractory disease who are being considered for single ASCT for relapsed disease. Patients must be eligible to undergo a stem cell transplant as per institutional criteria for selection at the time of registration.
- 3.13 The following laboratory values obtained ≤ 14 days prior to registration.
- Calculated creatinine clearance (using Cockcroft-Gault equation below)* ≥ 30 mL/min
 - Absolute neutrophil count (ANC) $\geq 1000/\text{mm}^3$
 - Platelet count $\geq 75 \times 10^9/\text{L}$ unless the participant has $\geq 50\%$ bone marrow infiltration in which case a platelet count of $\geq 50 \times 10^9/\text{L}$ is allowed
 - Hemoglobin ≥ 9.0 g/dL
 - Total bilirubin $\leq 1.5 \times$ the upper limit of the normal range (ULN) or if total bilirubin is $> 1.5 \times$ ULN, the direct bilirubin must be ≤ 2.0 mg/dL.
 - Alanine aminotransferase (ALT) and aspartate aminotransferase (AST) $\leq 3 \times$ ULN or $< 5 \times$ ULN if liver involvement

*Cockcroft-Gault Equation:

$$\text{Creatinine clearance for males} = \frac{(140 - \text{age})(\text{actual body weight in kg})}{(72)(\text{serum creatinine in mg/dL})}$$

$$\text{Creatinine clearance for females} = \frac{(140 - \text{age})(\text{actual body weight in kg})(0.85)}{(72)(\text{serum creatinine in mg/dL})}$$

- 3.14 Patients with measurable disease defined as at least one of the following:
- Serum monoclonal protein ≥ 1.0 g/dL by protein electrophoresis
 - ≥ 200 mg of monoclonal protein in the urine on 24-hour electrophoresis
 - Serum immunoglobulin free light chain ≥ 10 mg/dL AND abnormal serum immunoglobulin kappa to lambda free light chain ratio.
- 3.15 ECOG performance status (PS) 0, 1 or 2 ([Appendix I](#)).
- 3.16 Willing to provide informed written consent.
- 3.17 Negative pregnancy test done ≤ 7 days prior to registration, for persons of childbearing potential only.
- 3.18 Willing to follow strict birth control measures.
- Persons of childbearing potential, agree to one of the following:
- Practice 2 effective methods of contraception, at the same time, from the time of signing the informed consent form through 90 days after the last dose of study drug, AND must also adhere to the guidelines of any treatment-specific pregnancy prevention program, if applicable, OR

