 - Agree to practice true abstinence when this is in line with the preferred and usual lifestyle of the subject. (Periodic abstinence [e.g., calendar, ovulation, symptothermal, post-ovulation methods] and withdrawal are not acceptable methods of contraception.)

Persons able to father a child: even if surgically sterilized (i.e., status post-vasectomy), must agree to one of the following:

- Agree to practice effective barrier contraception during the entire study treatment period and through 90 days after the last dose of study drug, OR
- Must also adhere to the guidelines of any treatment-specific pregnancy prevention program, if applicable, OR
- Agree to practice true abstinence when this is in line with the preferred and usual lifestyle of the subject. (Periodic abstinence [e.g., calendar, ovulation, symptothermal, post-ovulation methods] and withdrawal are not acceptable methods of contraception.)

- 3.19a Negative human immunodeficiency virus (HIV), hepatitis B and C test.
- 3.19b Willing to follow the requirements of the Pomalyst REMS program.
- 3.19c Willing to return to enrolling institution for follow-up (during the Active Monitoring Phase of the study).
- 3.19d Willing to provide bone marrow samples under IRB#521-93 for correlative research purposes (see Sections 6.2 and 14.0).

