7.2 Treatment Schedule

	Doses and Schedule				
	Agent	Dose Level	Route	Day	Retreatment
Cycles 1-4 Induction (x 4 cycles)	Ixazomib	4 mg	PO	1, 8, 15	Every 28 days
	Pomalidomide	4 mg	PO	Days 1-21	Every 28 days
	Dexamethasone	40 mg	PO	1, 8, 15, 22	Every 28 days
Cycle 5 Transplantation ^{a,e,f}	Stem cell mobilization ^b followed by single ASCT				
Cycles 6-9 Consolidation ^c (x 4 cycles)	Ixazomib	4 mg	PO	1, 8, 15	Every 28 days
	Pomalidomide	2 mg	PO	Days 1-21	Every 28 days
	Dexamethasone	40 mg	PO	1, 8, 15, 22	Every 28 days
Cycles 10 and Beyond Maintenance (until progression or unacceptable toxicity) ^d	Ixazomib	4 mg	PO	1, 8, 15	Every 28 days

- SCT:** Can be performed per institutional practice. Stem cells collected and cryopreserved ahead of time or collected immediately prior to transplant can be used. Conditioning regimen preference left to the treating physician, but should not be enrolled in any additional therapy trials.
- If not previously collected and cryopreserved.
- If a patient previously has a dose reduction in induction, the consolidation phase will start and continue at reduced dose.
- Ixazomib maintenance would start at 4 mg unless dose has been previously reduced in the Induction or consolidation phase due to a non-hematologic toxicity specifically attributed to Ixazomib.
- Window period is 2-4 weeks between Induction and ASCT; 60-120 days between ASCT and Consolidation and 0-4 weeks between the Consolidation and Maintenance phases.
- Melphalan conditioning followed by stem cell infusion is being considered as 'cycle 5' for logistical reasons only. No additional toxicity data will be collected in the immediate post ASCT period until day 60-100 when the patient returns for routine post ASCT-reevaluation.

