8.0 Dosage Modification Based on Adverse Events

Strictly follow the modifications in this table for the first **two** cycles, until individual treatment tolerance can be ascertained. Individual drugs can be dose reduced as per the table below depending on the adverse event attribution. Thereafter, these modifications should be regarded as guidelines to produce mild-to-moderate, but not debilitating, side effects. If multiple adverse events are seen, administer dose based on greatest reduction required for any single adverse event observed. Reductions apply to treatment given in the preceding cycle and are based on adverse events observed since the prior dose.

NOTE: If either of pomalidomide or ixazomib is discontinued, the patient can continue on the other drugs, unless specified otherwise in the dose modification tables. If both are discontinued, the patient will go to event monitoring (Section 18.0).

ALERT: *ADR reporting may be required for some adverse events (See Section 10)8.1*

Dose Levels for each drug in the combination

(Based on Adverse Events in Tables 8.2-4)

NOTE: One drug can be reduced each time based on the drug most likely related to the toxicity observed.

Ixazomib (Days 1, 8, 15)		Pomalidomide (Day 1-21)		Dexamethasone (Days 1, 8, 15, 22)	
Starting dose	4 mg	Starting dose	4 mg	Starting dose	40 mg
-1	3 mg	-1	3 mg	-1	20 mg
-2	2.3 mg	-2	2 mg	-2	12 mg
-3	2.3 mg Days 1, 15	-3	1 mg	-3	4 mg
-4	Discontinue	-4	Discontinue	-4	Discontinue

If patients cannot tolerate dose level –3 of ixazomib AND pomalidomide they will go to event monitoring per Section 4.2. If dexamethasone is discontinued, the patient may continue treatment.

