10.55 Pregnancy, Fetal Death, and Death Neonatal

If a female subject (or female partner of a male subject) taking investigational product becomes pregnant, the subject taking should notify the Investigator, and the pregnant female should be advised to call her healthcare provider immediately. The patient should have appropriate follow-up as deemed necessary by her physician. If the baby is born with a birth defect or anomaly, a second expedited report is required.

Prior to obtaining private information about a pregnant woman and her infant, the investigator must obtain consent from the pregnant woman and the newborn infant's parent or legal guardian before any data collection can occur. A consent form will need to be submitted to the IRB for these subjects if a pregnancy occurs. If informed consent is not obtained, no information may be collected.

In cases of fetal death, miscarriage or abortion the mother is the patient. In cases where the child/fetus experiences a serious adverse event other than fetal death, the child/fetus is the patient.

NOTE: When submitting Mayo Expedited Adverse Event Report reports for "Pregnancy", "Pregnancy loss", or "Neonatal loss", the potential risk of exposure of the fetus to the investigational agent(s) or chemotherapy agent(s) should be documented in the "Description of Event" section. Include any available medical documentation.

10.551 Pregnancy

Pregnancy should be reported in an expedited manner as **Grade 3 "Pregnancy, puerperium and perinatal conditions - Other (pregnancy)"** under the Pregnancy, puerperium and perinatal conditions SOC. Pregnancy should be followed until the outcome is known.

If a woman becomes pregnant or suspects that she is pregnant while participating in this study or within 90 days after the last dose, she must inform the investigator immediately and permanently discontinue study drug. The sponsor-investigator must fax a completed Pregnancy Form to the Millennium Department of Pharmacovigilance or designee. If a female partner of a male patient becomes pregnant during the male patient's participation in this study, the sponsor-investigator must also immediately fax a completed Pregnancy Form to the Millennium Department of Pharmacovigilance or designee (see Section 10.43). Every effort should be made to follow the pregnancy for the final pregnancy outcome.

Suggested Pregnancy Reporting Form:

- Pregnancy Report Form

Use form available from the CTEP protocol development page:

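### The contraception period in nursing item 15.292 (4 weeks after pomalidomide stops) does not match the 90 days after the last dose used in 3.18 and 10.551

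*Combined protocol and SAP*

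**What the plan says.** **Nursing guidelines, 15.292.** Staff are to instruct patients that "certain precautions MUST be employed by all subjects on protocol and for 4 weeks after discontinuation of agent". The item belongs to Section 15.2, so the agent is pomalidomide. It covers donation and contraception; on the latter it says that "sexually active males/ females must use protocol-specific contraception (regardless of fertility status- i.e. history of vasectomy".

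**Eligibility, 3.18, persons of childbearing potential.** Those who choose contraception commit to two methods "from the time of signing the informed consent form through 90 days after the last dose of study drug". They must also follow any treatment-specific pregnancy prevention program. True abstinence is the alternative.

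**Eligibility, 3.18, persons able to father a child.** The first of three options is "Agree to practice effective barrier contraception during the entire study treatment period and through 90 days after the last dose of study drug, OR". The other two are following a treatment-specific program and true abstinence.

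**Pregnancy reporting, 10.551.** The notification duty applies to a woman who becomes or suspects she is pregnant "while participating in this study or within 90 days after the last dose, she must inform the investigator immediately".

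**Treatment schedule, 7.2.** Pomalidomide is scheduled in Cycles 1-4 and 6-9 only. Ixazomib then continues alone: "Cycles 10 and Beyond Maintenance (until progression or unacceptable toxicity". Section 8.0 adds that "If either of pomalidomide or ixazomib is discontinued, the patient can continue on the other drugs", unless the dose modification tables say otherwise.

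**The concern.** The protocol states the contraception period in two ways. One counts 4 weeks from stopping pomalidomide; the other counts 90 days from the last dose of study drug. In this regimen those starting events are different dates by design, because ixazomib maintenance follows the last pomalidomide cycle and pomalidomide can also be dropped early.

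The shorter period is the one printed where staff are told what to say to patients. Someone following 15.292 as written could release a patient from contraception inside the period that patient accepted at entry under 3.18, and inside the window in which 10.551 still expects a pregnancy to be reported. The protocol treats the risk as serious: 3.22 describes the fetal effects of the investigational agent as unknown, and 15.291 records teratogenicity of pomalidomide in rabbits.

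**Working it through.** There is no statistical figure to reproduce. The check compares the passages and counts days.

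**1. Length and starting event**

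| Place | Length | Counted from |
|---|---|---|
| 15.292 | 4 weeks = 28 days | pomalidomide stopped (and while on protocol) |
| 3.18, childbearing potential, contraception option | 90 days | last dose of study drug |
| 3.18, able to father a child, barrier option | 90 days | last dose of study drug |
| 10.551, notification | 90 days | last dose |

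**2. All drugs stopped on the same day.** 90 - 28 = 62 days.

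**3. Pomalidomide stopped on schedule.** Count days from Cycle 9 Day 1 = day 1. Inputs from 7.1 and 7.2:
- Last pomalidomide dose is on day 21, so the 4 weeks end on day 21 + 28 = 49.
- Cycle 9 lasts 28 days, or up to 56.
- Maintenance cycles last 28 days, with the last ixazomib dose on Day 15. After m maintenance cycles the last dose falls on day (Cycle 9 length) + 1 + 28(m - 1) + 14.
- With no maintenance, the last study drug is dexamethasone on day 22.

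Take the 15.292 precautions to apply throughout treatment, since the item says they hold on protocol. The post-treatment difference is then (last dose + 90) minus the later of day 49 and the last dose.

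| Course after Cycle 9 Day 1 | Last dose | 4 weeks end | 90 days end | Difference after treatment |
|---|---|---|---|---|
| No maintenance | 22 | 49 | 112 | 112 - 49 = 63 |
| 1 maintenance cycle, Cycle 9 = 28 days | 43 | 49 | 133 | 133 - 49 = 84 |
| 1 maintenance cycle, Cycle 9 = 56 days | 71 | 49 (passed) | 161 | 161 - 71 = 90 |
| 2 maintenance cycles, Cycle 9 = 28 days | 71 | 49 (passed) | 161 | 161 - 71 = 90 |
| 12 maintenance cycles, Cycle 9 = 28 days | 351 | 49 (passed) | 441 | 441 - 351 = 90 |

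The difference is therefore 62 to 90 days. By the second maintenance cycle at the latest, the 4 weeks are over before the last ixazomib dose, and 15.292 then supplies no post-treatment period.

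**4. Other nursing items.** The ixazomib items (15.191-15.199b) and the dexamethasone items (15.391-15.397) contain no contraception instruction. Nothing addressed to nursing staff in those sections corrects or extends the 4 weeks.

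**The case against.** The best defence is that 15.292 is a pomalidomide-specific rule, motivated by the drug's likeness to thalidomide, and that it defers to the protocol for the contraception itself. For persons of childbearing potential, 3.18 joins the 90 days and any pregnancy prevention program with AND. The requirements can thus be read as cumulative, and a patient who keeps to 3.18 after stopping all drugs together also satisfies 15.292. This softens the conflict without removing it. The reference to protocol-specific contraception describes what is to be used, while the only duration printed in the nursing guidelines is 4 weeks, and 15.292 does not present it as a minimum.

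Four stronger readings are tempting, and the documents do not support them:

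- **That contraception lapses during ixazomib maintenance,** making the gap the rest of maintenance plus 90 days. The item applies while the patient is on protocol, and a patient on protocol maintenance still is. The firm difference lies after treatment.
- **That 90 days is mandatory for both sexes.** For persons able to father a child it is one of three options joined by OR, and abstinence is open to both groups. The conflict is clearest for persons of childbearing potential who choose contraception.
- **That 15.292 is the only contraception instruction staff or patients receive.** Staff also have 3.18, 10.551 and the Pomalyst REMS requirements. The consent pages, and Appendix IV (cited in 7.5 for pomalidomide information), are not in the supplied text.
- **That the 4 weeks is the error.** The documents do not settle which period or starting event should govern.

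**Conclusion.** The inconsistency is real. Item 15.292 differs from 3.18 and 10.551 in both length and starting event. The post-treatment difference is 62 days if all drugs stop together, and reaches 90 days once the 4 weeks have run out during ixazomib maintenance. It is a matter of patient safety and internal consistency that should be corrected; it does not touch the sample size, significance level, power or primary endpoint.

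The figures assume that being on protocol means receiving protocol treatment, which the documents do not define, and that doses follow the schedule in 7.2. The conflict concerns contraception only, since 3.18 sets no donation period. A reader might infer that fetal exposure will follow, but the documents give no basis for estimating that. They do not say how many of the 25 planned patients have reproductive potential; they expect 8 women and cite a median age at onset of 65-70 years.

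**What to change.** Reconcile 15.292, 3.18 and 10.551 so that they state one period and one starting event, both chosen by the sponsor. Repeat that instruction in the ixazomib nursing guidelines (15.19), because ixazomib is the drug still being given after pomalidomide ends. When making the change, check that the consent form and Appendix IV agree. The cost is about one line in 15.292 and one in 15.19, plus any matching edit to 3.18 or 10.551 if the sponsor changes the period there. No new procedures, visits or data are needed.

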15.3 Dexamethasone for Oral Administration (DXM)

- 15.31 **Background:** Dexamethasone is an adrenal corticosteroid compound. Dexamethasone decreases inflammation by suppression of neutrophil migration, decreased production of inflammatory mediators, and reversal of increased capillary permeability; suppresses normal immune response. Dexamethasone's mechanism of antiemetic activity is unknown.
- 15.32 **Formulation:** Commercially available for oral administration as:
Tablets [scored]: 0.5 mg, 0.75 mg, 1 mg, 1.5 mg, 2 mg, 4 mg, and 6 mg
Solution, oral: 0.5 mg/mL (500 mL)
Solution, oral concentrate: Dexamethasone Intensol: 1 mg/mL (30 mL)
- 15.33 **Preparation, storage, and stability:** Refer to package insert for complete preparation and dispensing instructions. Store oral tablets at room temperature between 20°C to 25°C (60°F to 77°F). Protect from moisture. Dispense in a well-closed, light-resistant container as defined in the USP/NF. Store oral liquid at room temperature, do not freeze. Do not use if solution contains a precipitate. Refer to commercial package for drug expiration date.
- 15.34 **Administration:** Refer to the treatment section for specific administration instructions. May be taken with meals to decrease GI upset.
- 15.35 **Pharmacokinetic information:**
Onset of action: Prompt
Duration of metabolic effect: 72 hours
Metabolism: Hepatic
Half-life elimination: Normal renal function: 1.8-3.5 hours; **Biological half-life:** 36-54 hours
Time to peak, serum: Oral: 1-2 hours
Excretion: Urine and feces
- 15.36 **Potential Drug Interactions:**
Cytochrome P450 Effect: **Substrate** of CYP3A4 (major); **Induces** CYP2A6 (weak), 2B6 (weak), 2C8 (weak), 2C9 (weak), 3A4 (strong)
Increased Effect/Toxicity: Aprepitant, azole antifungals, calcium channel blockers, cyclosporine, estrogens, and macrolides may increase the serum levels of corticosteroids. Corticosteroids may increase the hypokalemic effects of amphotericin B or potassium-wasting diuretics (loop or thiazide); monitor. Refer to the package insert for a listing of other drugs.
Decreased Effect: Antacids and bile acid sequestrants may reduce the absorption of corticosteroids; may reduce the absorption of corticosteroids; separate administration by 2 hours. Aminoglutethimide, barbiturates, and CYP3A4 inducers may reduce the serum levels/effects of dexamethasone and dexamethasone may decrease the levels/effects of other CYP3A4 substrates. Serum concentrations of isoniazid may be decreased by corticosteroids. Corticosteroids may lead to a reduction in warfarin effect. Corticosteroids may suppress the response to vaccinations.
Ethanol/Nutrition/Herb Interactions:
Ethanol: Avoid ethanol (may enhance gastric mucosal irritation).
Food: Dexamethasone interferes with calcium absorption. Limit caffeine.
Herb/Nutraceutical: Avoid cat's claw (*Uncaria tomentosa*), echinacea (have immunostimulant properties)

- 15.37 **Known potential adverse events:** Consult the package insert for the most current and complete information.
- Common known potential toxicities,** frequency not defined:
Fluid and electrolyte disturbances, congestive heart failure in susceptible persons, hypertension, euphoria, personality changes, insomnia, exacerbation of infection, exacerbation or symptoms of diabetes, psychosis, muscle weakness, osteoporosis, vertebral compression fractures, pancreatitis, esophagitis, peptic ulcer, dermatologic disturbances, convulsions, vertigo and headache, endocrine abnormalities, ophthalmic changes, and metabolic changes. Some patients have experienced itching and other allergic, anaphylactic or hypersensitivity reactions. Withdrawal from prolonged therapy may result in symptoms including fever, myalgia and arthralgia.
- 15.38 **Drug procurement:** Commercial supplies. Pharmacies or clinics shall obtain supplies from normal commercial supply chain or wholesaler.
- 15.39 Nursing Guidelines:
- 15.391 Monitor patient regularly for hypertension, CHF and other evidence of fluid retention.
- 15.392 Advise patient of possible mood or behavioral changes, i.e., depression, euphoria, insomnia, even psychosis. Instruct patient to report any suspected changes to healthcare team.
- 15.393 Assess for symptoms of gastric ulcer, heartburn, or gastritis. Suggest antacids. Instruct patient to report symptoms to healthcare team if unable to control.
- 15.394 Evaluate signs of infection, particularly local candidal infections and treat appropriately.
- 15.395 Monitor blood glucose frequently.
- 15.396 Instruct patient to report frequent, unrelenting headaches or visual changes to healthcare team.
- 15.397 Advise patient that easy bruising is a side effect.

